**SA1. Community Advisory Board (CAB).** We will engage a CAB of 6-8 Mount Hope Cowboys (MHC) coaches and mothers to partner with us and guide decisions about intervention adaptation and refinement, including content and structure. Information will be solicited to guide the development of the in-person physical activity (PA) sessions (types of fitness activities, duration, etc.) before the intervention begins. Once underway, the CAB will provide input on issues related to intervention implementation and ideas for future refinement. Feedback will be provided via biweekly in-person or virtual meetings facilitated by Dr. [name] and a bilingual staff member. CAB meetings will be audio-recorded and detailed notes will be taken. CAB members will be incentivized \$200 (\$25 per meeting) for their time.

**SA2. Open Pilot Trial.** After modifying the intervention content and structure, we will then test it in an 8-week open pilot with a single group of 45 mothers (all receiving the intervention). The intervention will consist of in-person PA sessions (offered 3 times/week, with participants encouraged to participate at least twice), 2 goal setting sessions, and weekly written materials (e.g., brochures and tip sheets). Participants will complete 4 assessments (baseline, 4-weeks, 8-weeks (i.e., intervention end), and 1-month follow-up), the last of which will include an exit interview; 15 participants, chosen at random, will also be invited to complete an in-depth interview. Pre and post assessments and interviews will allow us to assess feasibility and acceptability (SA2a) and identify the potential impact of the intervention on mothers' PA (SA2b).

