**Intervention Description.** While the final content and structure of the intervention will be informed by Specific Aim 1, participants will receive a culturally adapted, Social Cognitive Theory (SCT) and Transtheoretical Model- (TTM) based PA intervention. The evidence-based, theory guided aerobic PA intervention will systematically builds upon our prior studies and includes the following components: Goal setting. At baseline, participants will complete an in-person or Zoom goal-setting session based on motivational interviewing where they will learn about the benefits of MVPA, key behavior change techniques such as goal-setting and self-monitoring and establish personal PA goals. They will be assisted in developing a plan for gradually building up to 150 minutes of MVPA per week over 8 weeks and will discuss potential barriers and learn problem solving skills. Any participants already meeting the 150 min/week MVPA guideline will be assisted in developing a plan for sustaining their PA and achieving other PA goals. Midway through the intervention, participants will complete a second goal-setting session. In-person PA sessions. Participants will be invited to participate in PA sessions during their child's practice. Sessions will be offered 3 days/week, and participants will be encouraged to attend at least 2 sessions/week during the 8-week intervention. Sessions will last for 50 minutes, with the intention that attending all 3 sessions per week would allow participants to meet the recommended 150 minutes of MVPA per week. The time of the sessions (i.e., whether in the middle, first, or second of hour of practice) will be informed by the CAB, with all sessions including aerobic activities that encourage MVPA (jogging, jumping jacks, etc.). Participants will learn about proper form, movement techniques, safety, and injury prevention, and be given demonstrations on how to properly do each exercise using their own body weight or basic equipment that will be provided (e.g., resistance bands, jump ropes, small weights). Childcare, with age-appropriate movement activities, will provided for mothers with additional children not practicing. The PA equipment will be gifted to the MHC at the end of the intervention for continued use by mothers during practice. Written materials. Participants will be emailed brochures and tip sheets weekly throughout the intervention. Materials include motivation-matched PA manuals (based on baseline and week 4 assessments), tip sheets (on stretching, boredom, places to be active, etc.) and computer expert system-tailored PA feedback reports which draw from a bank of over 330 messages targeting different levels of SCT and TTM constructs (motivational readiness, self-efficacy, self-

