**Measures.** Assessments, conducted at practice, will be used to examine intervention feasibility, acceptability, and satisfaction, and effects, and to provide data for the tailoring expert system to function. Intervention feasibility, acceptability, usability, and satisfaction. Feasibility will be determined based on whether enrollment (i.e., 10-12 participants per week), retention (i.e.,  $>80\%$  of participants through 8 weeks), and assessment (i.e., obtain usable PA data from  $>80\%$  of participants) targets are achieved. Acceptability will be determined based on participant engagement with the intervention during the study period (i.e.,  $>80\%$  of participants attended at least 2 in-person sessions per week) and by assessing the degree to which participants find the intervention beneficial using Likert-type scales. Satisfaction will be assessed using an adapted version of the Consumer Satisfaction Measure, used by our research team in past trials and adapted for this study, and the Client Satisfaction Questionnaire. The intervention will be deemed satisfactory if  $>80\%$  of participants report a "good" acceptability or higher. Participants will complete an exit interview to assess the acceptability of the intervention components, duration, and structure. They will also be asked which components they found most/least helpful, whether they would recommend the intervention to others if offered again, and if they felt the intervention had an impact. Primary outcome for examining intervention effects on PA. Participants will complete a **7-Day PAR Interview** at each assessment (baseline, 4-weeks, at the end of the intervention, and at 1-month follow-up) to assess minutes of MVPA per week. This self-report instrument provides an estimate of total weekly minutes of MVPA and has been used across many studies. It has consistently demonstrated acceptable reliability, internal consistency, and congruent validity with other more objective PA measures along with sensitivity to changes in both moderate and intensive levels of PA. Our team has extensive experience with administering this instrument, which requires annual recertification. Potential moderators and mediators. **Demographics**, assessed at baseline, include age, education, income, race, marital status, employment and occupation, country of birth, and length of residence in U.S. Other potential moderators and mediators include SCT and TTM constructs, which will also be assessed for the purposes of tailoring print materials. **Stages of Change for Physical Activity** measure has successfully been used to stage-match treatment in our trials and has shown acceptable reliability (Kappa = 0.78; intraclass correlation  $r = 0.84$ ) and concurrent validity with measures of self-efficacy and current PA levels. **Processes of Change for Physical Activity (POC)** measure contains 10 subscales that address a variety of cognitive/behavioral processes related to PA behavior change. Internal consistency of the subscales range from .62 to .96. **Self-Efficacy For Physical Activity (SE)** measures self-efficacy to become physically active across diverse contexts. The internal consistency is acceptable ( $\alpha = .82$ ). **Social Support for Exercise (SSE)** has three subscales (Family, Friends, Rewards/ Punishments) and acceptable internal consistency ( $\alpha$ s .61-.91) and criterion validity. **Physical Activity Enjoyment Scale (PACES)** assesses level of personal satisfaction from PA. The measure has high internal

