SA 2a. We will descriptively (means, proportions) analyze the post-intervention feasibility, acceptability, and satisfaction data. The qualitative exit interviews with participants will be audio recorded, transcribed, coded, and analyzed to determine how the intervention can be strengthened. The mixed methods findings will be used to refine the intervention content, structure, and assessments for future iterations of the intervention. SA 2b. Consistent with Aim 2b we will first examine within-person changes over time in PA outcomes (self-reported min/week of MVPA and a binary indicator of meeting national PA guidelines). Specifically, a longitudinal mixed effects model will regress min/week MVPA at end of treatment (8 weeks) and 1-month follow-up on baseline MVPA, time, and confounders identified a priori (e.g., age). Contrasts can be used to examine changes from baseline to 8 weeks in PA behavior, as well as changes 8 weeks to 1 month-follow up (to understand potential maintenance of behavior). Models will include a subject specific intercept to account for repeated measures within person over time. Next, a longitudinal model implemented with Generalized Estimating Equations with robust standard errors will be used to examine changes in meeting the national guideline of more than 150 min/week of MVPA over time controlling for baseline value of the indicator and potential confounders. This model will be specified to allow us to estimate whether the odds of meeting guidelines changed over time. In both cases (continuous and binary PA outcomes), interest is in estimating effect sizes rather than strict statistical hypothesis testing. Finally, a similar analytic strategy will be used to examine dose effects on both PA outcomes (by including a predictor in the model which counts the number of sessions attended/week). Models will be run using the fully enrolled sample under various assumptions of missing data and effects compared between models (for example, a multiple imputation approach vs. a likelihood-based approach to estimation).

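### SA 2b sets the binary activity outcome at strictly more than 150 min/week, while the intervention section counts exactly 150 as meeting the recommendation

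*Combined protocol and SAP*

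**What the plan says.** Data Analysis, SA 2b, first names the outcome without a number, as "a binary indicator of meeting national PA guidelines". The sentence on the GEE then supplies one: the model will "examine changes in meeting the national guideline of more than 150 min/week of MVPA over time". The indicator also enters that model as a covariate, since the estimate is to be obtained "controlling for baseline value of the indicator and potential confounders". Its purpose is to "estimate whether the odds of meeting guidelines changed over time". SA 2b then extends a similar strategy to dose effects on both the continuous and the binary outcome.

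Intervention Description uses the figure differently. It says "Sessions will last for 50 minutes", with the aim that "attending all 3 sessions per week would allow participants to meet the recommended 150 minutes of MVPA per week". The same section sets the goal-setting plan at 150 minutes a week and describes the guideline as 150 min/week, with no requirement to exceed it.

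The minutes come from the 7-Day PAR. Of it, Measures says: "This self-report instrument provides an estimate of total weekly minutes of MVPA". The section headed SA2 gives the sample size: the team will "test it in an 8-week open pilot with a single group of 45 mothers".

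**The concern.** The two sections disagree about a mother whose weekly total is exactly 150. Under Intervention Description she has met the recommendation; under SA 2b she has not. No other coding rule in the document settles the point, so two analysts working from the same plan could build two different indicators.

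The boundary value is not an arbitrary one. It is both the goal-setting target and the scheduled total for full attendance, and the outcome is self-reported, so totals of exactly 150 are plausible, although the document gives no count. The coding enters SA 2b in three places: the GEE outcome, the baseline covariate in that model, and the binary version of the dose-effect model. At stake is the definition of the quantity whose odds the GEE estimates. If the rule is left open, it could be chosen after the data have been seen.

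**Working it through.** **Inputs**

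- Session length 50 minutes, 3 sessions a week, recommendation 150 min/week (Intervention Description).
- Cut-off for the indicator: more than 150 min/week (Data Analysis, SA 2b).
- N = 45 (SA2, Open Pilot Trial), with models run on the full enrolled sample (Data Analysis, SA 2b).
- k, the number of mothers with a PAR total of exactly 150 at a visit: not given. Assumed range 0 to 3.

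**Step 1. Reproduce the plan's figure.** 3 x 50 = 150 min/week, which agrees with Intervention Description.

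**Step 2. Apply both rules to that figure.** 150 > 150 is false; 150 >= 150 is true. The strict and inclusive rules differ only at this value.

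**Step 3. Effect on the proportion at one visit.** Let a be the number above 150. The strict proportion is a/45 and the inclusive proportion is (a + k)/45, so strict minus inclusive = -k/45, whatever a is.

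| k (assumed) | Shift under the strict rule |
|---|---|
| 0 | 0 |
| 1 | -1/45 = -2.2 points |
| 2 | -2/45 = -4.4 points |
| 3 | -3/45 = -6.7 points |

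**Step 4. Effect on change between two visits.** Strict minus inclusive change = (k_earlier - k_later)/45. Three assumed cases show that the sign is open:

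- k goes from 0 to 3: (0 - 3)/45 = -6.7 points.
- k goes from 2 to 0: (2 - 0)/45 = +4.4 points.
- k is the same at both visits: 0.

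**Step 5. Odds at one visit, for illustration.** Suppose 15 of 45 are above 150 (assumed). The strict odds are 15/30 = 0.50.

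- k = 1: inclusive odds 16/29 = 0.552, ratio 0.552/0.50 = 1.10.
- k = 3: inclusive odds 18/27 = 0.667, ratio 0.667/0.50 = 1.33.

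These are crude odds at a single visit. The adjusted GEE odds ratio cannot be computed from the document.

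**Step 6. Fewer usable records.** Measures aims for usable activity data from more than 80% of participants. At 80%, 0.80 x 45 = 36, and one mother is worth 1/36 = 2.8 points instead of 2.2.

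**The case against.** The strongest reply is that the phrase is loose wording and not a coding rule. It describes the national guideline in passing, and the outcome is otherwise named only by reference to that guideline. Since Intervention Description gives 150 as the goal, as the guideline and as the full-attendance total, a careful analyst would probably count 150 as success. This is a fair reading and keeps the point minor. It does not remove it, because the only inequality written for the indicator is the strict one and nowhere is the inclusive rule stated.

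A second reply is that the full-attendance sentence states a design intention and does not define an outcome. Session time also covers technique, safety and demonstrations, so not all 50 minutes need be MVPA. The PAR covers the whole week, so activity outside sessions counts too. Full attendance therefore need not produce a total of exactly 150. That is correct, and the finding does not depend on it: the two sections conflict for anyone at exactly 150, however she got there.

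Third, little hangs on the choice. The percentage points rest on an assumed k that may be zero, and no direction of bias is shown. The plan seeks effect sizes and not strict tests, and no progression criterion uses the indicator. Because minutes are collected, either version can be derived later. All of this stands, and it limits the severity. Even so, an effect size for meeting the guideline depends on what counts as meeting it, and the rule should be fixed before the data are seen.

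**Conclusion.** The concern holds and is minor. SA 2b as written is inconsistent with Intervention Description at exactly 150 min/week, and would code as a failure a total that the programme treats as success. That the wording conflicts is certain; that any estimate will move is not. The size is 2.2 percentage points per mother at exactly 150 with 45 analysed, hence 0 to 6.7 points at a visit for an assumed 0 to 3 such mothers, with no predictable sign for change over time. The continuous min/week outcome and the feasibility, acceptability and satisfaction criteria in Measures are not touched. The conclusion rests on the document's own wording and not on any outside guideline text.

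**What to change.** In Data Analysis, SA 2b, replace the strict wording with an explicit rule: the indicator equals 1 when 7-Day PAR MVPA is at least 150 min/week (>= 150) and 0 otherwise. State that the same rule applies at every time point, so that it covers the GEE outcome, the baseline covariate and the dose-effect model. This agrees with Intervention Description, which then needs no edit. If the sponsor does intend the strict cut-off, the plan should say so deliberately, and the two sections should be reconciled before analysis.

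The cost is one phrase in the analysis plan. No new data are needed, and neither the intervention nor the study procedures change.
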